10.0 Study Timelines

10.1 Describe the anticipated duration needed to enroll all study subjects.

Response:

The duration need to enroll all participants is 19 months.

10.2 Describe the duration of an individual subject's participation in the study. Include length of study visits, and overall study follow-up time.

Response:

Each participant intervention is 1-2 months and it will take 30 – 45 minutes for each of 4 time assessments. From the beginning of the contact to the end of 4h assessments, it will be about 10 months.

10.3 Describe the estimated duration for the investigators to complete this study (i.e. all data is collected and all analyses have been completed).

Response:

2. 5 years

11.0 Setting

11.1 Describe all facilities/sites where you will be conducting research procedures. Include a description of the security and privacy of the facilities (e.g. locked facility, limited access, privacy barriers). Facility, department, and type of room are relevant. Do not abbreviate facility names.

NOTE: Examples of acceptable response may be: “A classroom setting in the Department of Psychology equipped with a computer with relevant survey administration software,” “The angiogram suite at Buffalo General Medical Center, a fully accredited tertiary care institution within New York State with badge access,” or, “Community Center meeting hall.”

Response:

Care recipients' home where OTGS can observe caregivers' difficulty in caring for the care recipients, or caregivers' home. All of them are located in either Erie County or Niagara County. Other activities will take place in a conference room in the Department of Rehabilitation Science at UB. The final assessment will be conducted through a phone call.

11.2 For research conducted outside of UB and its affiliates, describe:

- *Site-specific regulations or customs affecting the research*
- *Local scientific and ethical review structure*

NOTE: This question is referring to UB affiliated research taking place outside UB, i.e. research conducted in the community, school-based research, international research, etc. It is not referring to multi-site research. UB affiliated institutions include Kaleida Health, ECMC, and Roswell Park Cancer Institute.

Response:

Residential places where caregivers are members of the PACE. OTGS will be trained for safety and regulation at the PACE under the status of volunteer.

N/A: This study will not be conducted outside of UB or its affiliates.

12.0 Community-Based Participatory Research

12.1 Describe involvement of the community in the design and conduct of the research.

NOTE: Community-Based Participatory Research (CBPR) is a collaborative approach to research that equitably involves all partners in the research process and recognizes the unique strengths that each brings. CBPR begins with a research topic of importance to the community, has the aim of combining knowledge with action and achieving social change to improve health outcomes and eliminate health disparities.

Response:

N/A: This study does not utilize CBPR.

12.2 Describe the composition and involvement of a community advisory board.

Response:

N/A: This study does not have a community advisory board.

13.0 Resources and Qualifications

*13.1 Describe the qualifications (e.g., education, training, experience, expertise, or certifications) of the Principal Investigator **and** staff to perform the research. When applicable describe their knowledge of the local study sites, culture, and society. Provide enough information to convince the IRB that you have qualified staff for the proposed research.*

NOTE: If you specify a person by name, a change to that person will require prior approval by the IRB. If you specify a person by role (e.g., coordinator, research assistant, co-investigator, or pharmacist), a change to that person will not usually require prior approval by the IRB, provided that the person meets the qualifications described to fulfill their roles.

Response:

[name], Clinical Professor at the UB Department of Rehabilitation Science, School of Public Health and Health Professions is the PI. [name] possesses expertise in home-based exercise, function, and health behavior in older adults, and a record of accomplishment of conducting federally funded studies to improve older adults' health and quality of life through promoting their independence. She collaborated with the PACE in previous study on fall prevention. In addition, she authored two articles on international caregivers on individuals with Alzheimer's disease. Co-Investigator [name], Ed.D. OTR is an experienced geriatric occupational therapist whose specialty is fall prevention in older adults. Interviewers are all graduate level of occupational therapy students who completed occupational therapy courses and passed level I (1 week each) and level II (3 months) field work. They will be supervised by the PI and co-PI. Therefore, they are all qualified to conduct this research.

Describe other resources available to conduct the research.

13.2 Describe the time and effort that the Principal Investigator and research staff will devote to conducting and completing the research.

NOTE: Examples include the percentage of Full Time Equivalents (FTE), hours per week. The question will elicit whether there are appropriate resources to conduct the research.

Response:

The PI will spend 0.11 FTE and the Co-I will spend .05 FTE, extra in addition to regular student's project time (3 credits per semester). Since this project is tied with a students' mandatory research group project, students will spend regular time, 3 hours/week and extra 2% for this project for extra record keeping for this research purpose. In addition, a research assistant will spend 0.2 FET for two calendar years. These efforts were justified and accepted by the School and the grant giver.

Describe the availability of medical or psychological resources that subjects might need as a result of anticipated consequences of the human research, if applicable.

NOTE: One example includes: on-call availability of a counselor or psychologist for a study that screens subjects for depression.

Response:

The PACE has medical doctors, nurses, physical therapists, occupational therapists, a speech and language therapist, and a dentist. They will be available when specific relevant questions arise.

13.3 Describe your process to ensure that all persons assisting with the research are adequately informed about the protocol, the research procedures, and their duties and functions.

Response:

We set aside two months prior to start the project to make sure all parties are familiar with the protocol. Each OTGS will be tested by the PI for the procedure and how to communicate with caregivers, methods to collect data.

We will be communicating with rehab directors at the PACE. The PI will explain the protocol in detail to the rehab facility members in two meetings. The protocol has been accepted by three facilities of the PACE prior to submitting the grant proposal.

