One instrument (Positive aspect of caregiving) is only available in English. To fully understand caregivers' challenges and convey solutions, our current study OT graduate students are not competent enough in other languages to provide interventions. We do not have budget to hire interpreters.

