When the detailed challenges were documented, the OTGS may recommend some solutions, if she has, such as educating the process of Alzheimer's disease and suggesting an assistive device, good grip utensils.

At the end of the interview, the participant will be paid \$20.00.

The UB geriatric team including OTs, a gerontologist, and OTGS will brainstorm to develop solutions to identified problems. Within a week, these solutions will be presented to the participant and the OTGS and the participants will decide final solutions that the participant will perform. We use a caregiver-centered approach to facilitate their motivation to continue their care. The proposed approach will emphasize working collaboratively with caregivers to identify challenges and individualized strategies for each caregiver to solve specific problems. This is a different approach from the traditional therapist-client relationship, in which therapeutic prescriptions are made and provided by OTs to their clients.

Agreed-upon solutions will be reported to the PACE, especially if suggestions involve CRs. If assistive devices are needed, the PACE will provide them along with proper training for use.

Example interventions include: (a) didactic education about diseases; (b) the use of errorless techniques to improve assistance for CR's ADL,

IADL, and communication tasks; (c) the use of incentives (e.g., providing a favorite scented shampoo, going for an ice cream after going to a hair stylist, having a snack or short game to prevent going to bed right after dinner); (d) use of the Buffalo Functional Exercise for strengthening (a home-based exercise developed for PACE by the PI and shown to be effective in preventing falls, as reported by the NY Dept. of Health; attached); (e) use of a schedule/calendar on a computer, cell phone and/or blackboard in CR's home to coordinate caregiving tasks for family members; (f) suggesting more frequent PACE daycare visits or use of a nearby PACE-recommended daycare center; and (g) home safety suggestions using the Home Safety Self-Assessment Tool (HSSAT) to prevent falls in CR's home environment. We expect that more customized solutions will arise from this project.

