The data will be collected using a pen and paper and transferred to a computer software program (SPSS) file. The transferred data will be verified by an OTGS who is different from the data collector for missing data and correctness of data.

Confidentiality

A. Confidentiality of Study Data

Describe the local procedures for maintenance of confidentiality of study data and any records that will be reviewed for data collection.

*16.4 A. Where and how will all data and records be stored? Include information about: password protection, encryption, physical controls, authorization of access, and separation of identifiers and data, as applicable. Include physical (e.g. paper) **and** electronic files.*

Response:

Data in a paper form will be stored in a locked file cabinet in room [name] where only the PI can access with a key. This is separated from the identifiable information. Transferred data into SPSS will be stored in the UB Box, which is password protected and encrypted. Only study OTGS and PI can access the file with permission and a password.

The only link between personal identifiers such as name, address, phone number and data will be an ID number.

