16.6 A. Who will have access to the data?

Response:

The study OTGS who collect data and the PI.

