19.0 Risks to Subjects

19.1 List the reasonably foreseeable risks, discomforts, hazards, or inconveniences to the subjects related to their participation in the research. Consider physical, psychological, social, legal, and economic risks. Include a description of the probability, magnitude, duration, and reversibility of the risks.

NOTE: Breach of confidentiality is always a risk for identifiable subject data.

Response:

While being asked about depression in the past week, participants may be upset. We consider this as a minimal risk. But if the data shows that the participant is depressive, we will take an immediate action described above.

While a caregiver is helping the care recipient's activities of daily living using a new technique that are learned from us, such as a new transfer method, they may make a mistake and fall and have an injury. However, prevention of falls is one our study purpose.

19.2 Describe procedures performed to lessen the probability or magnitude of risks, including procedures being performed to monitor subjects for safety.

Response:

If a participant appears to be upset, the interviewer (OTGS) will ask if he/she would like to continue the interview or not. If they wants to continue after

a little rest, the interview will be resumed. If not, an interview at another time will be asked to complete the interview and make an appointment. In addition, if he/she scores 15 or more in the total CES-D, it will be informed to the participant and the PACE. The PACE may inform the PI about withdrawal of the participant from this study. We do not know the PACE criteria for the decision, but we will follow the PACE's decision.

Physical injury may occur while assisting care recipients' activities of daily living, but the purpose of the study is to prevent that. Any newly learned methods may cause discomfort or a fall, if the method is applied in a wrong way. Therefore, OTGS will show an intervention and caregivers will practice it until they become comfortable. An illustrated instruction will be provided for caregivers, if necessary or requested.

19.3 If applicable, indicate which procedures may have risks to the subjects that are currently unforeseeable.

Response:

Assisting transfer from a bed to a standing position and getting up from a couch.

If applicable, indicate which research procedures may have risks to an embryo or fetus should the subject be or become pregnant.

Response: N/A

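### The same student pool delivers the intervention and conducts the outcome interviews, and nothing keeps a caregiver's own student from collecting the self-reported primary outcomes

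*Combined protocol and SAP*

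**What the plan says.** **Who interviews.** Section 13.1: "Interviewers are all graduate level of occupational therapy students who completed occupational therapy courses". Section 19.2 uses the two terms as one: "the interviewer (OTGS) will ask if he/she would like to continue the interview or not" (OTGS are the occupational therapy graduate students). Section 16.6 A lists those with access to the data as "The study OTGS who collect data and the PI".

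**Who delivers.** In Section 9.1, after the team has worked on a case, "these solutions will be presented to the participant and the OTGS and the participants will decide final solutions". Section 19.2: "OTGS will show an intervention and caregivers will practice it until they become comfortable". Section 5.4 justifies the English-only restriction on the ground that "our current study OT graduate students are not competent enough in other languages to provide interventions", so the students are the intervention providers.

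**What is measured.** The primary endpoint (Section 2.1 under Scientific Endpoints) is reduction of caregiver burden and depression. Section 9.2 names the 12-item Zarit Burden Interview and the 20-item CES-D. Section 9.1 places these questions in a structured interview with the caregiver, and Section 17.4 gives face-to-face interviews as the source of the safety data, which are the CES-D scores. The final assessment is a phone call (Sections 9.1 and 11.1).

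**What separation exists.** Only one is described, in Section 16.3: transferred data are "verified by an OTGS who is different from the data collector". The plan mentions no masked or independent assessor, no self-completed form, and no rule assigning different students to delivery and assessment.

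**The concern.** A caregiver who has agreed a plan with a student and practised techniques under that student's guidance may be reluctant to tell the same student that nothing improved. A student who knows the arm and expects the programme to work may also prompt or record answers differently. Either effect would lower burden and depression scores without any change in the caregiver's state, which is the direction that hypothesis 3 in Section 1.2 predicts.

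The comparator is usual support (Section 3.1), so working out and carrying through solutions with a student belongs to the treatment arm. The bias is therefore likely to be larger there. Only the difference between arms matters for the comparison. The models in Section 16.1 (generalized estimating equations, or repeated-measures ANOVA with a between-group factor) see only the recorded scores and cannot separate such a difference from a true effect. The protection has to come from the way the interviews are assigned.

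**Working it through.** **Step 1: what the passages establish about roles.**
- Interviewing: students, as a group (Sections 13.1, 16.6 A, 19.2).
- Delivery: students, as a group (Sections 5.4, 9.1, 19.2).
- Baseline: Section 9.1 moves from one student who obtains consent to the same noun with a definite article for the problem discussion, early recommendations and agreement on solutions. This reads as one person in a continuing role.
- Posttest, 4-month interview and final call: Section 9.1 puts all three in the passive voice and names no one. Section 13.1 makes the interviewer a student, but not any particular student.

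Overlap is therefore shown for the pool. For an individual student and caregiver after baseline, it is permitted but not stated.

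**Step 2: reproduce the plan's sample size.** Inputs from Section 16.2: d = 0.65, directional hypothesis, alpha .05, power 80%. With the normal approximation,

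n per group = 2(z0.95 + z0.80)² / d² = 2(1.645 + 0.842)² / 0.65² = 12.37 / 0.4225 = 29.3, rounded up to 30.

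This matches the stated 30. The noncentral t distribution gives 80.0% power at 30 per group.

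**Step 3: effect of a net interviewing bias when the true effect is zero.** Let b be the difference in bias between arms, in SD units. The documents give no value for b, so 0.1 to 0.3 is an assumed range. For a two-sample t test with 30 per arm, df = 58 and the noncentrality is b × √(30/2) = 3.873b. The chance of a significant result favouring treatment is the upper tail of the noncentral t beyond the critical value: the 95th percentile for a one-sided .05 test, the 97.5th for a two-sided .05 test.

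| Assumed b (SD) | Noncentrality | One-sided .05 | Two-sided .05, tail favouring treatment |
|---|---|---|---|
| 0 | 0 | 5.0% | 2.5% |
| 0.1 | 0.387 | 10.3% | 5.7% |
| 0.2 | 0.775 | 19.0% | 11.5% |
| 0.3 | 1.162 | 31.0% | 20.7% |

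The normal approximation gives 10.4%, 19.2% and 31.5% for the one-sided column. Both columns are needed because Section 16.2 sizes the study on a directional hypothesis, while Section 16.1 sets .05 for the primary analyses without stating sidedness.

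**Step 4: scale.** A bias of 0.2 SD is 0.2 / 0.65 = 31% of the planned effect.

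**The case against.** **Same-student overlap is not documented.** A reader might infer from Section 9.1 that the treating student also gives the posttest and later interviews. The text does not say so, because no one is named for those assessments. This objection stands. The defect is an assignment left open, not a documented practice.

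**Bias need not be confined to the treatment arm.** A reader might infer that only treated caregivers would give courteous answers. The documents do not support that. Section 9.1 describes the in-depth problem discussion, and the option for a student to suggest solutions at the first interview, without restricting either by arm. Controls are also interviewed by students and paid after each interview. Some courtesy may cancel between arms, and early suggestions to controls could dilute the contrast. This also stands, so b must be read as a net difference. Its likely direction still follows from the usual-support comparator.

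**The figures are illustrative.** They come from a single-timepoint t test, not from the planned longitudinal models, and the size of b is assumed. They show what a given bias would do, not that it will occur.

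**Separating roles may not mask the assessor.** Section 9.1 puts students on the team that devises solutions, so a student who never met the caregiver may still know the case and therefore the arm. This stands and limits what the remedy can achieve.

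**The remedy may not be free.** Section 13.2 gives students 3 hours a week plus 2%, their number is not stated, and visits cover two counties. If an outcome interview would have shared a visit with intervention work, a different interviewer means another trip. This stands as a modest cost.

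**Conclusion.** The concern holds in a limited form. The plan uses one pool of students for delivery and for interviewing on self-reported primary outcomes, leaves the post-baseline interviewer unspecified, and describes no masking. That leaves the primary comparison open to courtesy and interviewer bias, probably in favour of treatment. With no true effect and an assumed net bias of 0.1 to 0.3 SD, the chance of a false positive favouring treatment would be roughly two to six times nominal one-sided, or two to eight times two-sided.

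The conclusion rests on three things: the plan's silence on who assesses whom, an inference from the usual-support control that bias would differ by arm, and an assumed size of bias. The documents do not show that bias will occur, that each caregiver's own student will conduct the later interviews, or that controls would be free of it.

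**What to change.** In Section 9.1, state who conducts each post-baseline assessment. Require that the 2-month, 4-month and final (10-month) interviews be done by an existing study student who
- has not worked with that caregiver,
- where feasible, did not take part in the team discussion of that case, and
- is not told the arm.

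Ask the scales before any discussion of solutions. The students are already trained and tested on data collection (Section 13.3), and Section 16.3 already assigns a different student to verify data, so swapping caseloads fits the existing staffing.

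The research assistant in Section 13.2 may look like a convenient caller for the final interview. That would conflict with Section 13.1 (interviewers are all students) and Section 16.6 A (data access), so it is not part of this recommendation.

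The cost is scheduling, some lost rapport and possibly an occasional separate trip. Masking will be imperfect. Caregivers will still know whether they received the programme, and separate interviewers cannot remove that source of bias. The plan should state it as a limitation.

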14.0 Other Approvals

14.1 Describe any approvals that will be obtained prior to commencing the research (e.g., school, external site, funding agency, laboratory, radiation safety, or biosafety).

Response:

We received funding from the Ralph Wilson Jr. Foundation between July 1st, 2017 and June 30th 2018. .. The revision/addition was requested by the evaluator of the foundation and approved on October 2nd, 2018.

N/A: This study does not require any other approvals.

15.0 Provisions to Protect the Privacy Interests of Subjects

15.1 *Describe how you will protect subjects' privacy interests during the course of this research.*

NOTE: Privacy refers to an individual's right to control access to him or herself. Privacy applies to the person. Confidentiality refers to how data collected about individuals for the research will be protected by the researcher from release. Confidentiality applies to the data.

Examples of appropriate responses include: "participant only meets with a study coordinator in a classroom setting where no one can overhear", or "the participant is reminded that they are free to refuse to answer any questions that they do not feel comfortable answering."

Response:

A participant only meets with a study interviewer in his/her designated place where no one can overhear and he/she are free to refuse to answer any questions that they do not feel comfortable answering. Therefore, participants' privacy will be protected.

15.2 *Indicate how the research team is permitted to access any sources of information about the subjects.*

*NOTE: Examples of appropriate responses include: school permission for review of records, consent of the subject, HIPAA waiver. This question **does apply** to records reviews.*

Response:

Obtaining the IRB and participants' permission in a consent form allows to access medical information revealed by the PACE, if it is necessary.

